## **Appendix 4 Standardized Protocol for Abdominal Ultrasounds**

A standardized protocol will be developed for all sites to follow regarding the minimal acceptable ultrasonography procedures to be performed. Please refer to the Imaging Manual.

Defibrotide (JZP-381)  
 Clinical Trial Protocol: 15-007 Version 4.0

Jazz Pharmaceuticals, Inc.  
 20 August 2018

## Appendix 5 Graft versus Host Disease Morbidity Assessment

### CHRONIC GRAFT-VERSUS-HOST DISEASE (GVHD) ASSESSMENT AND SCORING FORM

Page 1 of 2

Name: \_\_\_\_\_ Date of birth: \_\_\_\_\_ Assessment date: \_\_\_\_\_

	SCORE 0	SCORE 1	SCORE 2	SCORE 3
PERFORMANCE SCORE:  KPS ECOG LPS	 Asymptomatic and fully active (ECOG 0; KPS or LPS 100%)	 Symptomatic, fully ambulatory, restricted only in physically strenuous activity (ECOG 1, KPS or LPS 80-90%)	 Symptomatic, ambulatory, capable of self-care, >50% of waking hours out of bed (ECOG 2, KPS or LPS 60-70%)	 Symptomatic, limited self-care, >50% of waking hours in bed (ECOG 3-4, KPS or LPS <60%)
SKIN Clinical features:  Maculopapular rash  Lichen planus-like features  Papulosquamous lesions or ichthyosis  Hyperpigmentation  Hypopigmentation  Keratosis pilaris  Erythema  Erythroderma  Poikiloderma  Sclerotic features  Pruritus  Hair involvement  Nail involvement % BSA involved 	 No Symptoms/Manifestation	 <18% BSA with disease signs but NO sclerotic features	 19-50% BSA OR involvement with superficial sclerotic features "not hidebound" (able to pinch)	 >50% BSA OR deep sclerotic features "hidebound" (unable to pinch) OR impaired mobility, ulceration or severe pruritus
 Abnormality present but NOT thought to represent GVHD				
MOUTH Diagnostic/Distinctive features  Present  Absent	 No symptoms	 Mild symptoms with disease signs but not limiting oral intake significantly	 Moderate symptoms with disease signs with partial limitation of oral intake	 Severe symptoms with disease signs on examination with major limitation of oral intake
 Abnormality present but NOT thought to represent GVHD				
EYES Mean tear test (mm):  >10  6-10  ≤5  Not done	 No symptoms	 Mild dry eye symptoms not affecting ADL (requiring eyedrops ≤ 3 x per day) OR asymptomatic signs of keratoconjunctivitis sicca	 Moderate dry eye symptoms partially affecting ADL (requiring drops > 3 x per day or punctal plugs), WITHOUT vision impairment	 Severe dry eye symptoms significantly affecting ADL (special eyewear to relieve pain) OR unable to work because of ocular symptoms OR loss of vision caused by keratoconjunctivitis sicca
 Abnormality present but NOT thought to represent GVHD				
GI TRACT	 No symptoms	 Symptoms such as nausea, vomiting, anorexia, dysphagia, abdominal pain or diarrhea without significant weight loss (<5%)	 Symptoms associated with mild to moderate weight loss (5-15%)	 Symptoms associated with significant weight loss >15%, requires nutritional supplement for most calorie needs OR esophageal dilation
 Abnormality present but NOT thought to represent GVHD				

Defibrotide (JZP-381)  
 Clinical Trial Protocol: 15-007 Version 4.0

Jazz Pharmaceuticals, Inc.  
 20 August 2018

Name:

(continued) **CHRONIC GRAFT-VERSUS-HOST DISEASE (GVHD) ASSESSMENT AND SCORING FORM** Page 2 of 2

	SCORE 0	SCORE 1	SCORE 2	SCORE 3
LIVER	 Normal LFT	 Elevated Bilirubin, AP*, AST or ALT <2 x ULN	 Bilirubin >3 mg/dl or Bilirubin, enzymes 2-5 x ULN	 Bilirubin or enzymes > 5 x ULN
 Abnormality present but NOT thought to represent GVHD				
LUNGS†	 No symptoms	 Mild symptoms (shortness of breath after climbing one flight of steps)	 Moderate symptoms (shortness of breath after walking on flat ground)	 Severe symptoms (shortness of breath at rest; requiring O 2 )
 PFTs not done				
FEV1 				
DLCO 	 FEV1 > 80% OR LFS=2	 FEV1 60-79% OR LFS 3-5	 FEV1 40-59% OR LFS 6-9	 FEV1 ≤39% OR LFS 10-12
 Abnormality present but NOT thought to represent GVHD				
JOINTS AND FASCIA	 No symptoms	 Mild tightness of arms or legs, normal or mild decreased range of motion (ROM) AND not affecting ADL	 Tightness of arms or legs OR joint contractures, erythema thought due to fasciitis, moderate decrease ROM AND mild to moderate limitation of ADL	 Contractures WITH significant decrease of ROM AND significant limitation of ADL (unable to tie shoes, button shirts, dress self etc.)
 Abnormality present but NOT thought to represent GVHD				
GENITAL TRACT	 No symptoms	 Symptomatic with mild signs on exam AND no effect on coitus and minimal discomfort with gynecologic exam	 Symptomatic with moderate signs on exam AND with mild dyspareunia or discomfort with gynecologic exam	 Symptomatic WITH advanced signs (stricture, labial agglutination or severe ulceration) AND severe pain with coitus or inability to insert vaginal speculum
 Abnormality present but NOT thought to represent GVHD				

**Other indicators, clinical manifestations or complications related to chronic GVHD (check all that apply):**

 Weight loss	 Bronchiolitis obliterans	 Bronchiolitis obliterans with organizing pneumonia
 Esophageal stricture or web	 Pericardial Effusion	 Pleural Effusion(s)
 Nephrotic syndrome	 Peripheral Neuropathy	 Myasthenia Gravis
 Malabsorption	 Cardiac conduction defects	 Coronary artery involvement
 Eosinophilia >500/microliter	 Other: _____	 Ascites (serositis)
		 Polymyositis
		 Cardiomyopathy
		 None

Biopsy obtained:  Yes  No Organ system(s) biopsied: \_\_\_\_\_ GVHD confirmed by histology:  Yes  No

OVERALL severity of GVHD:  No GVHD  Mild  Moderate  Severe

Change from previous evaluation:  No prior or current GVHD  Improved  Stable  Worse  N/A (baseline)

Completed by: \_\_\_\_\_ Date form completed: \_\_\_\_\_

† Pulmonary scoring should be performed using both the symptom and pulmonary function testing (PFT) scale whenever possible. When discrepancy exists between pulmonary symptom or PFT scores the higher value should be used for final scoring. Scoring using the Lung Function Score (LFS) is preferred, but if DLCO (carbon monoxide diffusion capacity corrected for hemoglobin) is not available, grading using FEV1 (forced expiratory volume) should be used. The LFS is a global assessment of lung function after the diagnosis of bronchiolitis obliterans has already been established. The percent predicted FEV1 and DLCO (adjusted for hematocrit but not alveolar volume) should be converted to a numeric score as follows: > 80% = 1; 70-79% = 2; 60-69% = 3; 50-59% = 4; 40-49% = 5; < 40% = 6. The LFS = FEV1 score + DLCO score, with a possible range of 2-12.

Abbreviations: ECOG (Eastern Cooperative Oncology Group), KPS (Karnofsky Performance Status), LPS (Lansky Performance Status); BSA (body surface area); ADL (activities of daily living); LFTs (liver function tests); AP (alkaline phosphatase); ALT (alanine aminotransferase); AST (aspartate aminotransferase); ULN (upper limit of normal); LFS (Lung Function Score); N/A (not applicable).

F1011.5 3/10/06 sev

Source: <https://www.fredhutch.org/content/dam/public/Treatment-Suport/Long-Term-Follow-Up/GVHD-Morbidity-Assessment.pdf>

Defibrotide (JZP-381)  
Clinical Trial Protocol: 15-007 Version 4.0

Jazz Pharmaceuticals, Inc.  
20 August 2018

## Appendix 6 Seattle Children's Hospital Guideline for Maximum Blood Volumes

### Maximum allowable blood draw volumes:

PATIENT'S WEIGHT		TOTAL VOLUME	MAXIMUM mL IN ONE BLOOD DRAW	MAXIMUM mL IN A 30-DAY PERIOD
Kg	lbs	mL	2.5% of total blood vol	5% of total blood vol
1	2.2	100	2.5	5
2	4.4	200	5	10
3	6.6	240	6	12
4	8.8	320	8	16
5	11	400	10	20
6	13.2	480	12	24
7	15.4	560	14	28
8	17.6	640	16	32
9	19.8	720	18	36
10	22	800	20	40
11 thru 15	24 thru 33	880-1200	22-30	44-60
16 thru 20	35 thru 44	1280-1600	32-40	64-80
21 thru 25	46 thru 55	1680-2000	42-50	64-100
26 thru 30	57 thru 66	2080-2400	52-60	104-120
31 thru 35	68 thru 77	2480-2800	62-70	124-140
36 thru 40	79 thru 88	2880-3200	72-80	144-160
41 thru 45	90 thru 99	3280-3600	82-90	164-180
46 thru 50	101 thru 110	3680-4000	92-100	184-200
51 thru 55	112 thru 121	4080-4400	102-110	204-220
56 thru 60	123 thru 132	4480-4800	112-120	224-240
61 thru 65	134 thru 143	4880-5200	122-130	244-260
66 thru 70	145 thru 154	5280-5600	132-140	264-280
71 thru 75	156 thru 165	5680-6000	142-150	284-300
76 thru 80	167 thru 176	6080-6400	152-160	304-360
81 thru 85	178 thru 187	6480-6800	162-170	324-340
86 thru 90	189 thru 198	6880-7200	172-180	344-360
91 thru 95	200 thru 209	7280-7600	182-190	364-380
96 thru 100	211 thru 220	7680-8000	192-200	384-400

Based on blood volume of:

1 to 2 kg

100 mL/kg

(pre-term infant)

>2 kg

80 mL/kg

(term infant - adult)

This information is similar to that used by the Committee on Clinical Investigations at Children's Hospital in Los Angeles, and at Baylor College of Medicine in Dallas, TX.

Adapted by [name]. August 2001

Children's Hospital and Regional Medical Center Laboratory  
Seattle, WA

Source: [www.seattlechildrens.org/pdf/blood-volume-chart.pdf](http://www.seattlechildrens.org/pdf/blood-volume-chart.pdf)

Defibrotide (JZP-381)  
Clinical Trial Protocol: 15-007 Version 4.0

Jazz Pharmaceuticals, Inc.  
20 August 2018

---

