### 6.8.2.1 Laboratory Parameters

Clinical laboratory tests will include serum chemistry, hematology, and coagulation (Table 7). Collection frequency is outlined in the Schedule of Procedures and Assessments in [Appendix 1](#) and [Appendix 2](#). If a patient is at risk for exceeding maximal allowable blood draw limits (per Seattle Children's Hospital Guideline for Maximum Blood Volumes, [Appendix 6](#)), the blood draw schedules for laboratory assessments may be adjusted within the guidelines outlined in [Section 7](#) to ensure patient safety.

Clinical laboratory tests can be measured as part of the screening visit or within 14 days prior to the start of the screening window on a non-screening test if the test was performed as part of patient's routine standard of care. Therefore, if a patient's normal SOC labs include all labs required as screening labs for the protocol and are done within 28 days prior to baseline, these labs can be considered to serve as the patient's protocol-mandated screening labs, and elevated AST/ALT (> 2.5 times the upper ULN) or bilirubin (> 1.5 times the ULN) values therein can be considered as liver risk factors in the inclusion criteria for the study.

During the study, clinically significant changes in routine laboratory tests will be considered AEs ([Section 6.8.1.1](#)).

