## 7 STUDY ACTIVITIES

A schedule of study procedures and assessments for patients in the DP and BSC arms is provided in [Appendix 1](#). A schedule of study procedures and assessments for patients who develop VOD during the study and are administered rescue defibrotide is provided in [Appendix 2](#).

Throughout the study, if a patient in either arm, and during either phase of the study (prophylaxis phase or VOD treatment phase), is at risk for exceeding maximal allowable blood draw limits (per Seattle Children's Hospital Guideline for Maximum Blood Volumes [in the opinion of the investigator], [Appendix 6](#)), the blood draw schedules may be adjusted or eliminated within the following guidelines to ensure patient safety. The investigator must document in medical records the rationale for eliminating any protocol-mandated blood tests:

- Investigators can eliminate or discontinue PK sampling and/or biomarker sampling as a first option.
- If elimination or discontinuation of sampling for PK (first) and biomarker (second) assessments still leaves a patient at risk of exceeding blood draw maximums as per [Appendix 6](#), investigators can opt for a less rigorous schedule of laboratory assessments (serum chemistry, hematology, and coagulation testing). Under these circumstances, the

sampling schedule for laboratory assessments, to be based on local institutional practice, must include all of the following (at a minimum), during all time periods when daily or twice weekly laboratory assessments are otherwise required:

- Sampling for bilirubin testing to be performed daily (up to Day +30 post HSCT if hospitalized)
- Sampling for serum chemistry and hematology testing to be performed at least 3 times weekly
- Sampling for coagulation testing to be performed at least once weekly

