## Defibrotide (JZP-381)

Clinical Study Protocol: 15-007 Version 4.0

Jazz Pharmaceuticals, Inc.  
20 August 2018

Sparse PK analysis: For patients in the DP arm (weighing >15 kg) who are not included in the intensive PK population, blood samples will be collected as follows: on Day +7 post-HSCT, 1 sample at 2 hours after the start of the infusion (within  $\pm 15$  minutes before the end of infusion) and 1 sample during the 2-hour window after the end of infusion (exact time relative to infusion must be recorded); on Days +15 and +30 post-HSCT (for patients still receiving defibrotide) at 2 hours after the start of infusion (within  $\pm 15$  minutes before the end of infusion).

Note: If early hospital discharge occurs before Day +15 post-HSCT, the PK sample does not need to be obtained. Furthermore, PK sampling can be eliminated if investigator believes such sampling will compromise patient safety (Appendix 6). The investigator must document in medical records the rationale for eliminating any protocol-mandated blood tests.

r. In addition to baseline, Day +7, and Day+15 post-HSCT, biomarker plasma samples to evaluate plasma concentration of potential VOD biomarkers (which may include but will not be limited to VCAM1, vWF, L-ficolin, PAI-1, CRP, ANG2, thrombomodulin) and/or GvHD biomarkers (which may include but will not be limited to TNFR1, IL1RL1 [also known as ST2], and REG3 $\alpha$ ) will be collected upon diagnosis of acute GvHD and 14 days following diagnosis of acute GvHD, as applicable. Note: If hospital discharge occurs before the Day +15 post-HSCT visit, the biomarker sample may be obtained on the day of early discharge or at 1 of the twice weekly visits between early discharge and the Day +30 post-HSCT visit. Biomarker sampling can be eliminated if investigator believes such sampling will compromise patient safety (Appendix 6). The investigator must document in medical records the rationale for eliminating any protocol-mandated blood tests.

s. If discharged prior to Day +15 post-HSCT and not obtained on the day of discharge.

t. Patients <15 kg may have immunogenicity samples collected if it is determined by the investigator that the collection would not pose safety concerns or cause a need for transfusion.

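### Two 30-day limits in Protocol Appendix 6 break the table's own 5% rule: 64 mL at 21 kg (should be 84) and 360 mL at 80 kg (should be 320)

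*Protocol*

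**What the plan says.** Appendix 6 reproduces a hospital guideline on maximum blood volumes. Its single-draw and 30-day columns carry the headings "2.5% of total blood vol 5% of total blood vol". A note under the table gives the basis: 100 mL/kg for 1 to 2 kg and 80 mL/kg above 2 kg.

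The two rows in question are 21 to 25 kg, "1680-2000 42-50 64-100", and 76 to 80 kg, "6080-6400 152-160 304-360". Two other rows help to read them: 16 to 20 kg, "1280-1600 32-40 64-80", and 86 to 90 kg, "6880-7200 172-180 344-360".

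The protocol puts the table to use in several places:

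- Section 6.6.1 is mandatory: no biomarker sample is to be taken from a patient expected to go over the Appendix 6 maximum.
- Sections 6.6.2.1 to 6.6.2.3 (pharmacokinetics) and 6.7 (immunogenicity) ask sites to monitor patients against it. The pharmacokinetic sections let the investigator drop samples.
- Section 6.8.2.1 allows the laboratory schedule to be adjusted: "If a patient is at risk for exceeding maximal allowable blood draw limits".
- Section 7 says that "the blood draw schedules may be adjusted or eliminated within the following guidelines to ensure patient safety", with the risk judged by the investigator. Pharmacokinetic samples go first and biomarker samples second.
- Appendix 1, footnote r, is discretionary: "Biomarker sampling can be eliminated if investigator believes such sampling will compromise patient safety".

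**The concern.** A limit defined as a fixed percentage of a weight-based volume must rise with weight. As printed, the 30-day limit falls from 80 mL at 20 kg to 64 mL at 21 kg, and from 360 mL at 80 kg to 324 mL at 81 kg. Neither drop can come from rounding.

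The stake is practical rather than inferential. The protocol adopts these cells as blood-safety limits. A limit that is too low can lead a site to omit a sample that the rule would allow. A limit that is too high allows more blood to be drawn than the rule intends.

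**Working it through.** **Inputs** (all from Appendix 6): 80 mL/kg above 2 kg; single draw = 2.5% of volume; 30-day limit = 5% of volume, which is therefore twice the single-draw limit.

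**The rule reproduces the other ends of these rows and the comparison rows:**

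- 16 kg: 0.05 × 1280 = 64 (printed 64)
- 20 kg: 0.05 × 1600 = 80 (printed 80)
- 25 kg: 0.05 × 2000 = 100 (printed 100)
- 76 kg: 0.05 × 6080 = 304 (printed 304)
- 90 kg: 0.05 × 7200 = 360 (printed 360)

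**It does not reproduce two cells:**

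| Weight | Volume (mL) | 5% rule (mL) | 2 × single draw (mL) | Printed (mL) | Difference | Printed as % of volume |
|---|---|---|---|---|---|---|
| 21 kg | 21 × 80 = 1680 | 0.05 × 1680 = 84 | 2 × 42 = 84 | 64 | −20 mL (−23.8% of 84) | 64/1680 = 3.8% |
| 80 kg | 80 × 80 = 6400 | 0.05 × 6400 = 320 | 2 × 160 = 320 | 360 | +40 mL (+12.5% of 320) | 360/6400 = 5.6% |

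The printed volume and single-draw limit are right in both rows, so each error is confined to one 30-day number.

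**Whole table.** There are 10 single-weight rows and 18 range rows, so 10 + 2 × 18 = 46 weight end-points. With three volume columns that is 138 entries. Of these, 136 match the rules exactly, and the two above are the only mismatches. Each wrong value also appears correctly elsewhere in the column (64 at 16 kg, 360 at 90 kg), which would fit a copying slip.

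**When a cell could change a decision.** Take the 30 days from Study Day 1 with 5 days of conditioning, as the protocol assumes. That window ends at about Day +23, so Day +30 samples fall outside it. Samples triggered by acute GvHD or rescue treatment are not counted.

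- 21 kg child, DP arm, sparse schedule: pharmacokinetics 3 × 3 = 9, biomarkers 3 × 3 = 9, immunogenicity 10 + 5 = 15, total 33 mL. The remainder for all other draws is 64 − 33 = 31 mL as printed and 84 − 33 = 51 mL under the rule. The cell matters only if other draws average between 31/30 = 1.03 and 51/30 = 1.7 mL/day.
- 80 kg adult, DP arm, intensive schedule: pharmacokinetics (9 + 9 + 1) × 3 = 57, biomarkers 3 × 7 = 21, immunogenicity 15, total 93 mL. The remainder is 360 − 93 = 267 mL as printed and 320 − 93 = 227 mL under the rule. The cell matters only between 227/30 = 7.6 and 267/30 = 8.9 mL/day.

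Below each range neither limit binds; above it both do. The documents give no volumes for routine laboratory tests, so how often a patient falls in either range cannot be computed.

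**The case against.** The arithmetic is not in doubt, but three objections carry weight.

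*Provenance.* The table is adapted from an outside hospital chart that cannot be seen here, and the protocol text was read from PDF by a program. Each discrepancy is a single digit. A misread digit, or an error already in the chart, cannot be excluded. This stands, and it makes checking the PDF the first step. It does not remove the point if the cells are as printed, because the protocol adopts the table as its own limit.

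*Judgment, not a hard limit.* Outside Section 6.6.1 the table is applied at the investigator's discretion. The 5% heading, the 80 mL/kg note and the correct single-draw column each let a site find the right number. This also stands. The one mandatory use concerns biomarkers, which are an exploratory objective.

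*Reach.* Read literally, only patients at exactly 21 kg or exactly 80 kg are affected. The table does not say how to apply a range. If a site interpolated, which is an assumption, intermediate weights would be wrong too: at 22 kg, 64 + (100 − 64)/4 = 73 mL instead of 88 mL.

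A reader might infer from the smaller remainder at 21 kg (31 against 51 mL) that samples were lost, or from the 80 kg cell that patients were over-bled. The documents support neither. Those remainders depend on which samples are counted, routine laboratory volumes are not given, and no affected patient is shown.

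**Conclusion.** Wrong as written, and minor. The printed 30-day limit is 20 mL too low at 21 kg, which errs on the safe side, and 40 mL too high at 80 kg. The likely consequence at 21 kg is an occasional pharmacokinetic or exploratory biomarker sample omitted without need. At 80 kg the excess over the rule is permissive, but no harm is shown.

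A reader might also wonder whether endpoint data are at risk. They are not: even on the reduced schedule, Section 7 keeps bilirubin testing daily for hospitalized patients up to Day +30. Sample size, error control and the efficacy analyses do not depend on this table.

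The conclusion rests on two assumptions: that the extracted text matches the PDF, and that the column heading, not the two cells, states the intended rule. The second is well supported, since 44 of the 46 thirty-day entries follow the heading.

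**What to change.** Check both cells against the protocol PDF and, if it can be obtained, the hospital chart. If the values are as printed, change the 30-day entries to 84-100 for 21 to 25 kg and 304-320 for 76 to 80 kg. Add a note that the chart has been corrected to its own 5% rule.

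The cost is two cells and one note. Section 11.6 requires a formal amendment with IRB/IEC approval for any change, so this belongs in the next amendment and does not justify one of its own. There is one small downside: lowering the 80 kg limit by 40 mL could occasionally lead to an omitted pharmacokinetic or biomarker sample. Raising the 21 kg limit works the other way.

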1 LIST OF ABBREVIATIONS

Abbreviation	Term
AE	Adverse event
AUC	Area under the curve
BLQ	Below the limit of quantitation
BMI	Body mass index
BSC	Best supportive care
CDISC	Clinical Data Interchange Standards Consortium
CMH	Cochran-Mantel-Haenszel
CTCAE	Common Terminology Criteria for Adverse Events
DMC	Data Monitoring Committee
DP	Defibrotide prophylaxis
eCRF	Electronic case report form
EDC	Electronic Data Capture
EMA	European Medicines Agency
EPAC	Endpoint Adjudication Committee
FDA	Food and Drug Administration
GvHD	Graft-versus-host disease
HSCT	Hematopoietic stem cell transplant
ICH	International Council for Harmonisation
IRT	Interactive response technology
ISC	Independent Statistical Center
ITT	Intent-to-treat
IWRS	Interactive web response system
KM	Kaplan-Meier
MedDRA	Medical Dictionary for Regulatory Activities
MOD	Multi-organ dysfunction
NRM	Non-relapse mortality
PK	Pharmacokinetic
PT	Preferred term
SAE	Serious adverse event
SAP	Statistical Analysis Plan

SD	Standard deviation
SOC	System organ class
TEAE	Treatment-emergent adverse event
VAS	Visual analogue scale
VOD	Hepatic veno-occlusive disease
WHO	World Health Organization

2 MODIFICATION HISTORY

Version	Date	Description
Original 1.0	15MAY2020	
2.0	24NOV2020	
Section 5 was updated to describe the following changes in conduct of the planned analysis:
 
 • Clarify censoring rules for subjects who do not undergo HSCT • Add censoring rules for subjects who are diagnosed with VOD prior to HSCT • Clarify the definition of Baseline 
Section 10.1.2 was updated to correct the criteria for determining prior liver disease by removing the criterion of advanced stage neuroblastoma requiring myeloablative conditioning.
 
Section 16 was updated to account for differences in PK timepoints across protocol amendments for samples taken in subjects who developed VOD and received defibrotide rescue treatment.

3 PURPOSE

This Statistical Analysis Plan (SAP) provides a detailed and complete description of the planned statistical analyses for the final analysis of Study 15-007 to support the Clinical Study Report (CSR). Mock tables, listings, and figures shells will be provided in a separate supporting document.

This SAP complies with the International Council for Harmonisation (ICH) Harmonised Tripartite Guideline Topic E9, Statistical Principles for Clinical Trials. The current version is based on Protocol version 4.0 dated 20 August 2018.

Biomarker and immunogenicity analysis plans and results will be provided in separate documents.

All decisions regarding the final analysis of the study results, as defined in this SAP document, will be made prior to database freeze of the study data.

